## NARRATIVE SUMMARY

Suicide is the leading cause of death due to illness among Canadian youth, claiming more lives than any medical illness, including cancer. Suicide prevention is possible, and early intervention is urgently needed. Consistent with previous research highlighting the need for emergency department (ED) based suicide prevention strategies we previously showed that youth who present to the ED seeking help for suicide-related behaviours are at particularly high risk of eventual suicide after discharge. The standard of care for youth presenting with suicidal ideation and risk behaviour (SRB) to the ED is that the ED personnel places a referral to a community mental health agency (CMHA), or refers the patient back to their usual health care provider for ongoing care. This represents usual care (UC). It is common for the standard of care that (i) immediate service does not occur, as patients are often placed on wait lists; (ii) families are expected to make the CMHA contact there is often no follow through; (iii) the treatment provided does not include crisis management; and (iv) many youth are connected to therapists inexperienced with crises, all of which result in further ED re-visits for suicidal behaviour.

This study will examine the effectiveness of a previously-piloted, ED-based suicide prevention intervention using a randomized clinical trial design. We will determine whether our patient- and Family-centered Suicide Prevention Strategy added to usual care (F-SPS + UC) is more effective than enhanced usual care (EUC) in reducing suicide-related behaviors in 128 youth at high-risk of suicide. F-SPS is a 6-week, outpatient program that teaches participants to identify and challenge the thoughts, feelings and conflicts that suicidal youth experience, and teaches them skills to manage impulses effectively. Piloting by the SickKids team has established the feasibility and acceptability of the intervention. Enhanced usual care consists of 6 weekly telephone calls to ensure that the participant has connected with community resources suggested by the ED team and provide additional resources as needed. Rigorous evaluation will investigate the intervention for an effect on suicide-related behavior and mental health crises (primary outcomes), mental health symptoms, patient/family functioning, economic costs, scale up/implementation feasibility and intervention fidelity (secondary outcomes). The proposed study is novel, in that it is the **first clinical trial of a youth suicide intervention in Canada**; it is efficient, in that it leverages the research-base and therapeutic infrastructure of a highly experienced child health team; and it is important, in that it targets the prevention of recurrent suicide attempts and of suicide, a leading cause of death. This study will be the first step toward developing an effective suicide prevention program that can be scaled-up and implemented across Ontario and Canada, to provide youth at high risk of suicide access to effective, evidence-based treatment, regardless of the community in which they live.

## BACKGROUND

Suicide is the second leading cause of death among youth in Canada, responsible for 1 in 4 deaths among adolescents aged 15 to 19 years in 2011. Indeed in Canada, more youth take their own lives than die by cancer and the top 10 fatal diseases in this population combined. Suicide also has profound implications for families and communities and incurs massive societal costs, estimated at 2.4 billion dollars per year in Canada. For these reasons, suicide is of considerable national and global significance, and is a priority area of the Mental Health Commission of Canada (MHCC) and the World Health Organization. Many advocates argue that truly addressing this massive problem requires that suicide is recognized as fulfilling the criteria for a specific mental disorder. Despite the enormity and the gravity of youth suicide nationally, Canada, unlike other developed countries, lacks a national youth suicide prevention strategy.

To our knowledge, this study is the first controlled clinical trial of an intervention to prevent suicide among high-risk adolescents in Canada.

Despite the widespread appeal of primary suicide prevention programs, successes have been limited. In fact, studies examining trends have identified increasing suicide rates among Canadian females between 1980 and 2008, with both males and females experiencing an increase in the medical severity of their emergency department (ED) presentations for suicide-related behaviours since 2004. For every completed suicide in Canada there are 20 to 40 attempts. The majority (90%) of youth who attempt suicide either have an underlying mental illness that is commonly undetected and untreated or they are at risk of emergence of a psychiatric disorder in young adulthood (e.g. schizophrenia, depression or bipolar disorder, anxiety disorder or personality disorder). Unlike more violent methods of suicide (e.g., firearms), which are frequently fatal, drug overdose has high survival rates. Two recent Ontario studies led by [name] (Co-PI) reported on the associations between self-harm attempts and completed suicide in the general population and in adolescents (n= 20,471). More than 99.9% of adolescents who presented to the ED with intentional overdose survived to discharge. However, roughly 1 in 100 of them died by suicide, compared to 1 in 3,500 matched peers from the general population, within a median interval of 7.2 years. Also, a recent review of systematic reviews carried out by Bennett et al (with co-I PS) concluded that the ED is likely the most promising site for the introduction of an effective suicide prevention strategy. Taken together, these data confirm that adolescents presenting to the ED following a suicide attempt are at high risk of having a previously undetected emerging mental illness, are at increased risk of suicide, and provide a very promising opportunity for secondary suicide prevention and early detection of mental illness through the use of an effective suicide prevention strategy (SPS).

There is presently an urgent unmet need for effective SPSs for high-risk youth, to prevent suicide and also to reduce suicidal SRBs which are common and frequently precede subsequent manifestations of mental health morbidity, impairment, and their resultant economic impacts. Because of the strong association between mental illness, particularly depression, and suicide, some researchers have targeted depression (or other underlying mental disorder) among youth in order to improve suicidality. However, several of these interventions have been ineffective in decreasing SRBs. As such, interventions aimed at improving mental health have not been shown to reduce SRBs for high-risk youth.

The current study is informed by available data examining the effectiveness of direct SPSs among youth. One systematic review (2011) of youth suicide-prevention intervention studies for high-risk youth noted that of 15 RCT's, only 1 reported effects on SRB, and that overall, methodological weaknesses (e.g. risk of bias, report of outcome data) limit interpretation of the data and progress in the field. When effective, SPSs involved lengthy (6 -12 months) therapies, which are impractical in the current Ontario fiscal environment, and report participation rates as low as 50%. Conversely, ultra-brief interventions (e.g. single session or telephone follow-up) have not been effective in decreasing SRBs as they are likely of insufficient duration and depth to yield therapeutic benefit. It was further demonstrated that an effective SPS for adolescents must include a family component in order to impact suicidal behaviour. This is consistent with the large literature that has highlighted family conflict as a particularly salient risk factor for SRB among adolescents. In a study comparing three months of weekly family-based therapy (FBT) for 66 suicidal adolescents, FBT led to greater reductions in suicidal thinking and depressive symptoms compared with treatment as usual. However, the study had several important weaknesses: assessors were not blinded to intervention status, suicide attempts were not captured, and the sample consisted of predominantly (~75%) very low income African-American families; all considerations that may limit validity of the study and its generalizability to an Ontario context.

The present study addresses both the practical and the methodological limitations of previous research in several ways. First, it targets the most vulnerable, high-risk adolescents (those with SRB), as identified by

data we have generated. Second, it incorporates the key therapeutic components previously shown to be possibly effective. Third, it optimizes treatment duration and intensity, as an immediate-access, 6-week intervention. Fourth, the intervention is evaluated using an innovative, rigorous Randomized Control Trial (RCT) design, thereby maximizing potential therapeutic benefit, acceptability, scalability and confidence in the study results. Fifth, by defining suicide as a disorder, and intervening early on the outcome of SRBs directly, the present study is consistent with leading edge conceptualization and prevention strategy for this highly impairing, and frequently fatal, mental health condition among youth.

## **STUDY GOALS, SPECIFIC AIMS, HYPOTHESES**

Youth who present to the ED with a suicide attempt often suffer from an underlying mental illness that is neither detected nor treated. These youth are at high risk of poor mental health outcomes in young adulthood, including repeat suicide attempts and death. There is an urgent need for an effective suicide prevention strategy, based in the ED, to facilitate early intervention for, and prevention of, youth suicide. Consistent with the Four-Point Plan for Suicide Prevention recently outlined in the journal Nature, RCT (1) defines suicide as a distinct disorder, (2) has a focused prevention strategy aimed at a high-risk population (youth with SRB), (3) utilizes rigorous methodology, and (4) targets early suicide-related outcomes directly.

### **Objectives:**

The primary objective of this study is to determine the effectiveness of a novel, ED-based, Focused Suicide Prevention Strategy combined with usual care (F-SPS + UC) in reducing suicidal ideation and risk behaviours (SRB).

The secondary objectives are to compare these treatment arms to assess the effect of F-SPS on (2a) symptoms of mental illness; (2b) level of functional impairment; (2c) family communication; (2d) cost effectiveness; (2e) and to examine fidelity of intervention delivery; and potential barriers and facilitators to subsequent implementation and scale-up, should the F-SPS prove to be cost-effective.

In future, we would like to follow these participants into adulthood, and examine the effectiveness of the F-SPS over a longer period of time using ICES data. This study will provide the preliminary results needed to inform a large, externally-funded, youth suicide prevention study that will enable a longer period of follow-up into adulthood.

### **Research Question:**

Among youth 12-18 years of age, presenting with SRB to the ED, does a focused suicide prevention strategy added to usual care (F-SPS + UC) lead to decreased SRB in the 6 month follow-up, as compared with enhanced usual care (EUC)?

### **Hypothesis**

1. To determine the effect of a Focused Suicide Prevention Strategy added to usual care (F-SPS + UC) on SRB. Hypothesis 1 (H1): Compared with EUC, we hypothesize that the F-SPS + UC will be effective in decreasing SRBs over the 6-month follow up period.
2. To examine the effect of F-SPS + UC on future acute mental health crises (ED and unscheduled health care visits). Hypothesis 2 (H2): Compared with EUC, we hypothesize that participants who

receive the F-SPS + UC intervention will have significantly fewer acute mental health crises.

## **METHODS**

### **Design:**

This is a single centre, single-blinded RCT of an F-SPS intervention with EUC in high-risk youth who present to the ED with suicidality.

### **Participant Selection**

Youth ages 12 to 18 years who present to the ED at Sick Kids with acute suicidal ideation or behaviour (including suicide attempt), and who provide informed consent, will be randomized to F-SPS + UC or EUC.

#### *Inclusion criteria:*

1. Youth presenting in the Emergency Department with SIQ-Jr score  $\geq 31$ ,
2. Has a participating parent or caregiver who is able to communicate easily in English, or is willing to communicate using a hospital-organized translator,
3. Between the ages 12-18 years old,
4. Living in the greater Toronto area and access to a telephone.

#### *Exclusion criteria:*

1. Score of 3 on KSADS screen for current psychosis or elevated mood
2. Moderate to severe intellectual disability, and/or autism based on clinical chart.

### **Procedure:**

The clinical research nurse in the ED will conduct a pre-screen of patients admitted to the ED using the Emergency Department Information System (EDIS), identifying patients within the eligible age range (12 – 18 years old) who present with SRB. A clinical nurse who is a part of the patient's circle of care will ask the youth and parent(s) or caregiver for permission to be approached about research. If the youth and parent(s) or caregiver give permission then the clinical staff will introduce the research nurse who will conduct a screening assessment to determine whether the youth is eligible. The assessment will consist of a clinical interview for psychosis and two self-report measures for suicidal ideation and behaviour. If the youth is eligible for the study then the nurse will alert the study research coordinator. . If the patient is eligible the clinical research nurse will review the consent or assent with the youth and parent(s), who will consent separately for their involvement with the Family-based component of the intervention. If both the youth and parent(s) or caregiver sign consent forms, then they will be enrolled into the study. It will be considered as refusal if one of the two parties does not consent, and they will not be enrolled in the study.

The study coordinator will contact the participant by telephone within a business day of their discharge from the ED to review the study procedures and to book their study assessment visits at baseline, to occur within two weeks of the index ED visit. They will also book their study visits six weeks post-randomization, and 24 weeks post-randomization. The study assessment visits will be completed either at SickKids or at the participant's home, depending on availability. The study coordinator will then randomize the participant to receive either to the F-SPS intervention + UC arm or EUC arm.

The study therapist will contact the participants randomized to receive the F-SPS intervention + UC arm and scheduled for their first treatment. The study coordinator will contact participants randomized to the EUC arm and schedule their EUC first phone call, and will provide resources to the child and family.

The research assistant will be responsible for administering outcome measures at study assessment visits, and will therefore be blinded to treatment allocation. We cannot blind the study coordinator, study therapist or families to treatment allocation.

In total there are four study visits. Participants will be assessed once by the study nurse at screening (the time of presentation in the ED), once by the study coordinator at baseline, and twice by the research assistant at 6 weeks post-randomization (at post-intervention), and 24 weeks post-randomization. Please see Table 1 for a complete measure administration schedule.

**Treatment allocation (F-SPS+UC or EUC):** Participants will be randomized to either receive the intervention, in addition to usual care (F-SPS+UC), or EUC only. They will be assigned in a 1:1 ratio of F-SPS+UC to EUC.

We will audio record F-SPS sessions if both the youth and the parent(s) or caregiver consent. These sessions will be reviewed by the principal investigators and the study staff in order to ensure fidelity to the treatment model.

In order to determine whether F-SPS+UC or EUC is related to a patient's health care service use, an analysis of participants' emergency room visits and unexpected medical appointments will also be conducted. OHIP numbers will be obtained at consent to link to ICES databases. .

We will recruit 128 adolescents to be randomized (64 adolescents per treatment arm) for this study (see 4.3 "Power Analysis").

**Intervention: F-SPS + UC (i)** is a manualized program that addresses the most common thoughts, feelings and conflicts that suicidal youth experience and teaches coping and safety skills to adolescents and their families. The program is the result of 3-years of development and quality improvement led by the PI ([name]), developed collaboratively with youth, families, and therapists. The program will be administered once weekly over 6 weeks by a trained therapist on an outpatient basis. Sessions consist of 1-hour spent one-to-one with the youth, followed by 1-hour with the youth and parent(s) or caregiver.

The therapist provides the youth and parent(s) or caregiver with a manual to use both during and between sessions. The program and manual address sources of conflict, ways to improve communication and ensure safety. The program resembles the only ED-based adolescent and family programs that have demonstrated effectiveness in decreasing suicidality. It is tailored to address the key concerns of the adolescent or family including mental health, academic problems, social or family conflict, acculturation issues, gender concerns or other stressors.

Participants will also have access to the UC recommended by the ED circle of care. The F-SPS program will not interfere with the youth's ongoing plan of care. The F-SPS therapist will communicate with the youth's UC provider following the completion of the intervention, and provide detailed information about the intervention to the UC provider. This communication ensures that the UC provider is also informed about the challenges and strategies for the participant, so that the UC therapist is better able to assist the participant should similar situations reoccur in the future.

**Comparator: Enhanced Usual Care.** The comparator arm consists of weekly telephone checks for six weeks following the ED visit in addition to the UC recommended by the ED circle of care. The study coordinator will also contact parents in the comparator arm by telephone once weekly for six weeks. They will review changes to the youth's usual care and their contact with community resources in the 7 days prior to the phone call. As such, the aim of the EUC comparator is to improve access to mental health resources. It is not a therapeutic intervention in and of itself. The study coordinator will provide further information regarding community mental health resources as needed. If the parent indicates that the youth is in immediate risk for suicidal behaviour, 911 will be called. The ED team's referral suggestions plus weekly telephone follow-up represents EUC.

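### The protocol does not place randomisation after the baseline visit, so baseline values of the secondary measures can be collected after allocation is known

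*Protocol*

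**What the plan says.** The Procedure section of the protocol gives the steps in this order:

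1. "The study coordinator will contact the participant by telephone within a business day of their discharge from the ED".
2. The purpose of that call includes "to book their study assessment visits at baseline, to occur within two weeks of the index ED visit".
3. "They will also book their study visits six weeks post-randomization, and 24 weeks post-randomization".
4. After a sentence on where assessment visits are held: "The study coordinator will then randomize the participant to receive either to the F-SPS intervention + UC arm or EUC arm".
5. "The study therapist will contact the participants randomized to receive the F-SPS intervention + UC arm and scheduled for their first treatment". The coordinator does the equivalent for the first EUC call.

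On blinding: "We cannot blind the study coordinator, study therapist or families to treatment allocation". The coordinator also carries out the baseline assessment. On the length of treatment: "The program will be administered once weekly over 6 weeks by a trained therapist on an outpatient basis". On follow-up, participants are seen "twice by the research assistant at 6 weeks post-randomization (at post-intervention), and 24 weeks post-randomization". The comparator paragraph counts the six weeks of EUC calls from the ED visit.

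Table 1 marks YSR, LPI, CIS, CBQ, CBCL and CALS at Baseline, week 6 and week 24, and HCUS at Baseline and week 24. It marks SIQ-Jr and SBQ-R at Screening and leaves their Baseline cell empty, whereas the Measures section says both are completed at baseline.

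**The concern.** The sequence reads as call, booking, randomisation, then treatment scheduling. The word *then* cannot mean after all the booked visits, since these include week 24. Visits dated from randomisation can be booked on the call only if the randomisation date is known or imminent. An EUC clock that starts at the ED visit also fits early allocation. The baseline visit, however, may be as late as day 14.

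A site that follows the text this way meets one or more of three problems:

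- **Baseline after allocation.** Youth and parents who know their arm report the pre-treatment values of the secondary scales. Expectation or disappointment can enter those values, and so can early treatment if it has begun. They are then no longer a clean starting point for change or a clean covariate.
- **Loss before baseline.** A randomised family unhappy with its arm can leave before giving any value on these scales, although the analysis is to be by intention to treat.
- **Week 6 during treatment.** If the first session is held back until a late baseline visit, the week-6 clock is already running, and the visit called post-intervention can fall before the last session.

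**Working it through.** **The plan's own figure.** The sample size does not bear on this point, but it reproduces. With SD 14 and difference 7 (d = 0.5), two-sided 0.05 and 80% power, the t-test needs 63.8, so 64 per arm and 128 in total (power 80.1%). Changing the order of events leaves it unchanged.

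**Inputs from the protocol.** The ED visit is day 0. The call is within one business day, so about day 1. Baseline is by day 14. Sessions are weekly and there are six. The week-6 visit is 42 days after randomisation.

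**Assumptions.** Discharge is on day 0. Randomisation (R) is at the call, on day 1, or on day 3 over a weekend. The date of the first session (S) is also assumed, because the protocol gives none.

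**Formulas.**
- Week-6 visit = R + 42.
- Sixth session = S + 35.
- The sixth session is on or before the week-6 visit when S + 35 ≤ R + 42, that is, when S − R ≤ 7 days.

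**(a) Treatment starts promptly, baseline on day 14, R = 1.** Baseline is 14 − 1 = 13 days after allocation.

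| First contact | Contacts before day 14 | Number |
|---|---|---|
| F-SPS session, day 2 | days 2, 9 | 2 |
| F-SPS session, day 4 | days 4, 11 | 2 |
| F-SPS session, day 8 | day 8 | 1 |
| EUC call, day 2 | days 2, 9 | 2 |
| EUC call, day 7 | day 7 | 1 |

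**(b) Treatment waits for baseline, both on day 14.** Sessions fall on days 14, 21, 28, 35, 42 and 49.
- R = 1: the visit is on day 43. Five of six sessions are done, and the sixth is 49 − 43 = 6 days after the visit.
- R = 3: the visit is on day 45, and the sixth session is 4 days after it.

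**(c) Neither timing fault.** With R = 1 and baseline and first session both on day 7, the sixth session is on day 42 and the visit on day 43. Treatment does not precede baseline and the course is complete by the visit. Baseline still follows allocation.

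**With randomisation at or after baseline.** No baseline value follows allocation. The sixth session falls 7 days before the week-6 visit if the gap from randomisation to first session is 0 days, on the same day if it is 7, and 1 day after if it is 8. One mismatch becomes visible: with randomisation on day 14, the week-6 visit is on day 14 + 42 = 56, while six weeks of EUC calls counted from the ED visit end on day 42.

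**The case against.** The strongest reply is that the order is left open, not fixed as allocation first. *Then* directly follows a sentence about completing assessment visits and could mean after the baseline visit. Baseline is dated from the ED visit while later visits are dated from randomisation, which suits a baseline that comes first. Table 1 puts Baseline ahead of Week 1. The study flow diagram is not shown and might settle the matter. This stands: a reader might infer that the protocol orders randomisation before baseline, and it does not say so. But Table 1 has no randomisation column, and no visible sentence rules out allocation first.

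Four further inferences are tempting and not supported:

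- **That the primary analysis is compromised.** SIQ-Jr is an ED eligibility score, the Procedure section places the two suicidality self-reports in the screening assessment, and Table 1 agrees. The covariate is exposed only if the Measures section governs instead.
- **That the arm difference shrinks by a stated percentage.** This would need a covariate coefficient, a pattern of benefit over sessions and first-session dates, none of which is given. YSR, CBCL and CBQ also look back six months at baseline, so at most about 13 of some 180 days would follow allocation.
- **That the unblinded K-SADS depression interview biases a change score.** It is taken only at baseline and has no follow-up value.
- **That one of the two treatment-timing faults must occur.** Case (c) shows otherwise.

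**Conclusion.** The point holds as a gap in the stated sequence. The protocol does not require baseline to precede randomisation, and its most natural reading permits the reverse. The firm exposure is to the measures marked at Baseline and repeated later: YSR, LPI, CIS, CBQ, CBCL, CALS and HCUS. These supply secondary outcomes on symptoms, functioning and family communication, and service-use data.

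In size, baseline can follow a day-1 randomisation by up to 13 days, with one or two contacts before it. If treatment waits for a baseline more than 7 days after randomisation, the sixth session comes after the week-6 visit, by 4 to 6 days in the examples. These figures rest on the assumed randomisation and first-session dates. The direction and amount of any bias cannot be quantified from the document. Because the primary covariate is probably taken in the ED before allocation, this should be corrected but does not by itself threaten the primary result.

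**What to change.** State in the Procedure section: *Randomisation takes place only after all baseline measures have been completed and before any F-SPS session or EUC call; the week-6 and week-24 visit dates are set from the date of randomisation.*

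Reconcile three other places with that order:

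- the comparator paragraph, which counts EUC calls from the ED visit while the follow-up visits are counted from randomisation;
- the description of week 6 as post-intervention, since the new sentence alone does not guarantee that the sixth session precedes that visit;
- the Measures section and Table 1, which disagree on whether SIQ-Jr and SBQ-R are first taken at baseline or at ED screening.

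The cost is protocol wording; no visit or staff are added. Allocation comes some days later for some families, which must be weighed against the Background's description of the intervention as immediately accessible. Booking baseline early within the existing two-week window limits that delay. Families who never attend baseline would not be randomised and would have to be replaced from those screened.
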